## 5.3. SUBJECT WITHDRAWAL AND/OR DISCONTINUATION

Any subject who wishes to may withdraw from the investigational product use or from participation in the study of his or her own accord for any reason is entitled to do so without obligation. The Investigator may also withdraw any subject from the investigational product use or from study participation, if deemed necessary.

Investigational product use may be discontinued and any subject may be discontinued from study participation at any time during the study at the discretion of the Investigator or the sponsor for any reason including but not limited to:

1. Occurrence of any medical condition or circumstance that exposes the subject to substantial risk and/or does not allow the subject to adhere to the requirements of the protocol.
2. Any SAE, clinically significant AE, severe laboratory abnormality, intercurrent illness, or other medical condition that indicates to the Investigator that continued participation is not in the best interest of the subject.
3. Subject's decision to withdraw.
4. Any woman who becomes pregnant while participating in the study. Information on the pregnancy and outcome will be requested.
5. Subject's failure to comply with protocol requirements or study related procedures.
6. Termination of the study by the Sponsor, FDA, or other regulatory authorities.

In the event study discontinuation of a randomized subject is necessary, the Investigator should make every attempt to have subject complete Visit 6 assessments as possible. If a non-serious AE is unresolved at the time of the subject's final study visit, an effort will be made to follow up until the AE is resolved or stabilized, the subject is lost to follow-up, or there is some other resolution of the event. The Investigator should make every attempt to follow all serious adverse events (SAEs) to resolution. The reason for premature discontinuation should be entered onto the Case Report Form (CRF) and recorded in the subject chart.

Subjects who withdraw from the study will not be replaced.

Additionally, the trial or parts of the trial may be discontinued by the sponsor or at the recommendation of the Investigator after consultation with Kala Pharmaceuticals, Inc. This may be based on a significant number of AEs of a similar nature that warrant such action.

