#### 5.1.8. Early Termination Visit

In the event of termination prior to Visit 6, every attempt will be made to ensure that all Visit 6 assessments are performed. If this is not feasible, at least the following should be performed/assessed:

- Use of any concomitant medications since the last visit
- Occurrence of any AEs since the last visit
- Used and unused investigational product collected and compliance [REDACTED]

- [REDACTED]
- BCVA
- Slit lamp biomicroscopy
- IOP measurement

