## 5.2. RESCUE MEDICATION USE

Any subjects not responding adequately to the study medication may be rescued and placed on alternate therapy at the Investigator's discretion at any time. The choice of rescue medication is at the Investigator's discretion. Any subject placed on rescue therapy will discontinue use of the study medication and continue study participation through Visit 6. Rescued subjects will be considered treatment failures, but the need for rescue therapy will not be considered an AE. Rescued subjects experiencing an AE at the time of rescue will be followed through stabilization or resolution of the AE or the end of the study (whichever comes last). Rescued subjects should not be withdrawn from the study, but rather followed to resolution of signs and symptoms or until the Investigator has deemed the subject is stable.

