#### 9.1.2. Analysis of Efficacy

The primary analysis population will be the Intent-to-Treat (ITT) population, defined as all subjects randomized. A subset of efficacy analyses will be examined for the Efficacy Evaluatable (EE) population, the definition of which will be outlined in the Statistical Analysis Plan and finalized prior to unmasking of study data pursuant to clinical data review.

The primary analysis of all ophthalmic efficacy measures will be based on the single study eye for each subject.

The co-primary endpoints are (1) the mean bulbar conjunctival hyperemia score at Visit 6; and (2) the mean [REDACTED] severity score averaged over the days from Visit 5 to the day before Visit 6.

Secondary and exploratory efficacy endpoints will be evaluated as elaborated in [Section 3](#).

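### Section 5.3 permits ending study follow-up, not only product use, for non-compliance, which can leave avoidable and possibly treatment-related gaps in the co-primary data

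*Combined protocol and SAP*

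**What the plan says.** Section 5.3 of the protocol treats product use and study participation as two things, either of which can be ended: "The Investigator may also withdraw any subject from the investigational product use or from study participation, if deemed necessary". It then widens the power: "any subject may be discontinued from study participation at any time during the study at the discretion of the Investigator or the sponsor". The grounds are open-ended. Six are listed as examples, and the fifth is "Subject's failure to comply with protocol requirements or study related procedures". Nothing in the visible text confines non-compliance to stopping product or keeps such a subject on the visit schedule. Withdrawn subjects are not replaced.

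Two provisions soften this. Section 5.3 adds that "the Investigator should make every attempt to have subject complete Visit 6 assessments as possible", and Section 5.1.8 says: "In the event of termination prior to Visit 6, every attempt will be made to ensure that all Visit 6 assessments are performed". If that is not feasible, Section 5.1.8 gives a reduced minimum set, part of which is redacted.

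Section 5.2 handles a different post-randomization event differently. A rescued subject stops study medication and stays in through Visit 6: "Rescued subjects should not be withdrawn from the study".

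On the analysis side, Section 9.1.2 makes ITT the primary population, "defined as all subjects randomized". The co-primary endpoints are hyperemia at Visit 6 and symptom severity averaged from Visit 5 up to the day preceding Visit 6. Section 9.4 handles missing co-primary data by multiple imputation under MAR, with the reasons for missingness and any imbalance between groups to be evaluated. The visible text names no analysis that departs from MAR.

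**The concern.** Non-compliance happens after randomization, and treatment can influence it through tolerability or perceived lack of benefit. If it leads to loss of follow-up, the ITT population keeps the subject but loses the outcome. The analysis must then fill the gap from subjects who were not removed, plus whatever earlier data the removed subject left. Where removal is related to treatment in ways that the earlier data do not capture, the estimate drifts from the effect in everyone randomized toward the effect in those who complied.

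This loss is avoidable. The remaining visits are already on the schedule, the trial lasts four weeks after randomization, and the protocol already follows rescued subjects to Visit 6. An analysis restricted by compliance would not require ending anyone's follow-up, since Section 9.1.2 already provides for a separate Efficacy Evaluable population.

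**Working it through.** **1. What is lost, by time of leaving** (visit days from Section 5.1, endpoints from Section 9.1.2)

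| Participation ends | Visit 6 hyperemia | Diary average, Visit 5 to the day before Visit 6 |
|---|---|---|
| Before Visit 4 (Day 15) | Early value at termination if obtained, otherwise missing; no Visit 4 value | None |
| Visit 4 to before Visit 5 (Day 22) | As above, but a Visit 4 value exists | None |
| Visit 5 to before Visit 6 (Day 29) | Early value if obtained, otherwise missing | Partial |

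The nominal diary window is Days 22 to 28, so 28 − 22 + 1 = 7 days. The early value also raises a question of use. Section 5.1.7 has the Visit 6 eCRF completed when a subject discontinues at an unscheduled visit. No visible rule says whether that value counts as the Visit 6 endpoint or is set aside and imputed.

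**2. The plan's sample size**

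Inputs: 71 per group, 90% power, two-group t-test, two-sided (Section 9.2). The effect size and alpha are redacted there, so 71 cannot be reproduced from stated inputs. Section 9.3 tests each co-primary endpoint at 0.05, and I assume that alpha here. Back-solving:

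- Normal approximation: d = (1.960 + 1.282) × √(2/71) = 3.242 × 0.1678 = 0.544.
- Exact t-test: d = 0.548. An assumed 0.55 returns n = 71 and 90.2% power, so the figure is coherent with an effect near 0.55 SD.
- Other alphas (t-test): 0.494 at 0.10 and 0.597 at 0.025.

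**3. Illustrative bias**

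Let m be the share of the active arm removed. Assume that those who remain show effect d, those removed have vehicle-like true outcomes, no one is removed from the vehicle arm, and imputation recovers none of the difference. Then the true ITT effect is (1 − m) × d, the estimate is d, and the overstatement is m × d.

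| Assumed alpha | d | m = 5% | m = 10% |
|---|---|---|---|
| 0.05 | 0.548 | 0.027 | 0.055 |
| 0.10 | 0.494 | 0.025 | 0.049 |
| 0.025 | 0.597 | 0.030 | 0.060 |

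If those removed kept half the drug benefit, the overstatement would halve: at d = 0.55, 0.014 SD for m = 5% and 0.028 SD for m = 10%.

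**4. Illustrative precision**

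Planned 150 less 2 × 71 = 142 leaves 8 subjects, and 8/150 = 5.3%. With an assumed effect of 0.55 SD and 75 per arm, t-test power on observed subjects is 91.7% with no loss, 90.3% at 5%, 88.7% at 10% and 84.8% at 20%. The documents state no loss rate, so all of these are assumptions.

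**The case against.** The strongest reply is that this is a discretionary clause in a short trial that already screens for compliance. That is largely fair:

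- Inclusion criterion 3 requires at least 80% product compliance in the last run-in week, and Section 4.1.2 excludes subjects judged unwilling or unable to comply. Non-compliers should be few. The run-in product is vehicle, however, so it cannot screen for problems specific to the active drug.
- Inadequate response has its own route in Section 5.2, where follow-up continues. This narrows the lack-of-benefit mechanism but does not close it, because rescue is also discretionary.
- Multiple imputation is not a completer mean. It can draw on a subject's own Visit 4 hyperemia and diary entries, so the bias in step 3 is an upper figure under its assumptions.
- A subject who already skips diaries or visits may not supply them when asked again. This stands, and it limits what the fix can recover.

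Four stronger readings are tempting, and the documents do not support them:

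- A reader might infer that non-compliers leave the ITT population. They do not; they stay in it and lose only outcome data.
- A reader might infer that both co-primary outcomes go missing by rule. Removal is optional, no compliance threshold triggers it, Visit 6 assessments are to be attempted, and a subject leaving after Visit 5 has part of the diary window.
- A reader might infer that Section 5.3 mandates the reverse of Section 5.2. It only allows it.
- A reader might infer that losing more than 8 subjects breaks the design. Section 9.2 does not describe 142 as a minimum number of completers, and power declines slowly with loss.

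**Conclusion.** The point holds as a gap in a permissive clause. Section 5.3 lets follow-up end for non-compliance. The attempted Visit 6 assessments reduce the resulting loss but cannot supply a Day 29 value or a full diary window. The plan then depends on MAR for subjects whose removal may be related to treatment.

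The likely size is modest: roughly 5% to 10% of the assumed effect, and only if 5% to 10% of the active arm is removed, those subjects would have fared as on vehicle, and imputation corrects none of it. The effect of about 0.55 SD behind these figures is inferred from 71 per group, not stated. The case for change rests less on that size than on the loss being avoidable and impossible to recover after database lock.

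**What to change.** In Section 5.3, separate ending product use from ending study follow-up, in both the general discretion clause and item 5. Changing item 5 alone would leave the gap open, because the general clause allows discontinuation for reasons beyond the list. State that:

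- non-compliance alone does not end follow-up;
- unless consent is withdrawn, the subject is asked to continue the diary and attend the scheduled Visit 6 (Day 29 ± 1);
- data collected this way are used in the ITT analysis.

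Decisions about dosing and safety-based discontinuation stay as written.

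The cost is a wording change plus some follow-up effort for a few subjects at visits already scheduled. Some of them may still not provide data.

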#### **5.4.        COLLECTION OF DATA**

Source documentation for data collected in this study will be maintained at the investigative site. In cases where no source will be used [REDACTED] it will be noted in the Investigator files. The CRF will be electronic (eCRF) and data will be electronically entered from the source documentation into the eCRF. After study completion, an archival copy [e.g., Portable Document Format (PDF)] of the eCRF data will be retained by the site.

## 6. TREATMENT OF SUBJECTS

### 6.1. INVESTIGATIONAL PRODUCTS TO BE ADMINISTERED

All subjects meeting eligibility criteria at Visit 1 will receive 2 bottles of single-masked investigational product (vehicle). Subjects who continue to meet eligibility criteria at Visit 2 will be randomized to either KPI-121 0.25% ophthalmic suspension or vehicle. One kit of randomized investigational product containing 3 dropper bottles will be allocated to each subject at Visit 2. At Visit 2 (Day 1/Randomization), subjects will receive 2 bottles of double-masked investigational product (KPI-121 0.25% ophthalmic suspension or vehicle). At Visit 4 (Day  $15 \pm 1$  day), subjects will receive 1 additional bottle of double-masked investigational product from the kit allocated. All bottles will be returned to the site at Visit 6 (Day  $29 \pm 1$  day). The investigational product will be stored at the site in a secure area with limited access at controlled room temperature (15-25°C/59-77°F).

Subjects will be asked to administer investigational product QID. Prior to each instillation, subject will be instructed to shake investigational product bottle. The subjects will record the time of administration of each dose of investigational product at the time of instillation ([Appendix 12](#)). Compliance with instillation of investigational product will be reviewed and assessed at each clinic visit.

### 6.2. CONCOMITANT MEDICATIONS

All medications that the subject has taken 6 months prior to Visit 1 and through Visit 6 or discontinuation from the study will be recorded in the eCRF and the subject chart. The generic name of the drug, dose, route of administration, duration of treatment (including start and stop dates), frequency, indication, and whether or not the medication was taken due to an AE will be recorded for each medication.

#### 6.2.1. Permitted Medications

Medications not specifically excluded in [Section 6.2.2](#) may be taken as necessary.

#### 6.2.2. Medications Not Permitted

At **Visit 1 (Screening)** and for the duration of the study:

- Any topical ophthalmic medications including eyelash growth medications, eye drops, gels, or artificial tears
- TNF-blocking agents (e.g. etanercept, adalimumab, infliximab)
- Treatment for glaucoma

Within **30 days** prior to screening (Visit 1) and for the duration of the study:

- Ocular, inhaled, or intranasal corticosteroids
- Ocular or oral non-steroidal anti-inflammatory drugs (NSAIDs)
- Topical ocular antibiotics
- Topical ocular antihistamines or mast cell stabilizers
- Oral antihistamines
- Topical or nasal vasoconstrictors
- Other investigational products

Within **60 days** prior to screening (Visit 1) and for the duration of the study:

- Topical cyclosporine (Restasis®)
- Any form of topical LE

Within **30 days** prior to the screening visit (Visit 1) alteration to the dose or anticipated alterations to the dose of the following are disallowed:

- Tetracycline compounds (tetracycline, doxycycline, or minocycline)
- Omega-3 or Omega-6 supplements

Within **6 months** prior to the screening visit (Visit 1) alterations to the dose or anticipated alterations to the dose of the following are disallowed:

- Anticholinergics
- Antidepressants
- Isotretinoin
- Oral corticosteroids
- Systemic immunosuppressive agents

### **6.3. INVESTIGATIONAL PRODUCT USE COMPLIANCE**

Compliance will be assessed by comparing investigational product accountability records with the [REDACTED]. The site will document this comparison along with verification of the numbers of used and unused investigational product bottles. The numbers of missed doses as assessed at each clinic visit should be documented in the eCRF.

### **6.4. DRUG ACCOUNTABILITY**

Sponsor study monitors or designees will conduct accountability of investigational product (KPI-121 0.25% ophthalmic suspension or vehicle). Accountability will be ascertained by

performing reconciliation between the amount of drug sent to the site and the amount used and unused at the time of reconciliation.

Clinical trial materials will be shipped to the investigational sites under sealed conditions. Investigational product shipment records will be verified by comparing the shipment inventory sheet to the actual quantity of drug received at the site. Accurate records of receipt and disposition of the investigational product (e.g., dates, quantity, subject number, dose dispensed, returned) must be maintained by the Investigator or his/her designee.

Investigational product will be stored at controlled room temperature (15-25°C/59-77°F) in an area limited to controlled access.

At the end of the study, all study materials, including any unused investigational products (KPI-121 0.25% ophthalmic suspension or vehicle), as well as original containers (even if empty), will be returned to the drug-packaging vendor in accordance with sponsor or designee's Standard Operating Procedures (SOPs), following approval by the Sponsor. All returns of investigational product will be documented. The study monitor or designee will verify drug accountability. All drug accounting procedures must be completed before the study is considered complete.

#### **6.5. MAINTENANCE OF RANDOMIZATION AND PROCEDURE FOR BREAKING THE CODE**

The sponsor, the project teams at the designated Contract Research Organizations (CROs), and investigative staff responsible for assessments of study endpoints will be masked to investigational product assignments. A dosing coordinator, who is not responsible for study assessments, will be required to dispense and retrieve investigational product to the subjects. In case of medical emergency, or occurrence of an SAE, the randomization code may be unmasked and made available to the Investigator, sponsor, and/or other personnel involved in the monitoring or conduct of this study. In the absence of medical need, the randomization code will not be available to the above individuals until after the study is completed and the database is locked.

In the event of a medical need, the Investigator will treat each subject as needed. Since there is no specific antidote to KPI-121, immediate emergency unmasking is not necessary. If the Investigator feels it is necessary to unmask a subject's assignment after an emergency situation, the Investigator may call the medical monitor and notify the sponsor. The investigational product assignment will be revealed on a subject-by-subject basis with the approval of the medical monitor and sponsor, thus leaving the masking of the remaining subjects intact.

A randomization code will be computer-generated by Kala Pharmaceuticals, Inc. or designee. Randomization team members will work independently of other team members at the CRO. Study personnel involved in subject assessment (i.e., not the dosing coordinator), study subjects, the sponsor, and project teams at the CROs involved in the study will be masked to investigational product assignments.

## 7. ASSESSMENT OF EFFICACY

Efficacy assessments include the following:

- Investigator-rated assessment of bulbar conjunctival hyperemia
- [REDACTED] severity assessment
- [REDACTED] frequency assessment
- Subject-rated assessment of ocular discomfort severity
- Subject-rated assessment of ocular discomfort frequency
- [REDACTED]
- Corneal fluorescein staining
- Lissamine green conjunctival staining

## 8. ASSESSMENT OF SAFETY

### 8.1. SAFETY PARAMETERS

Safety parameters include:

- Assessments of AEs
- BCVA
- Slit lamp biomicroscopy
- Dilated ophthalmoscopy
- IOP measurement

### 8.2. ADVERSE EVENT DEFINITIONS

**Adverse Event (AE):** Any untoward medical occurrence associated with the use of an investigational product in humans, whether or not considered drug related.

**Adverse Reaction (AR):** any AE caused by a drug. Adverse reactions are a subset of all suspected adverse reactions where there is reason to conclude that the drug caused the event.

**Suspected Adverse Reaction (SAR):**

Any AE for which there is a reasonable possibility that the drug caused the AE. For the purposes of IND safety reporting, “reasonable possibility” means there is evidence to suggest a causal relationship between the drug and the AE. A SAR implies a lesser degree of certainty about causality than adverse reaction, which means any AE caused by a drug.

**Unexpected:** An AE or SAR is considered “unexpected” if it is not listed in the Investigator’s Brochure or is not listed at the specificity or severity that has been observed; or, if an Investigator’s Brochure is not required or available, is not consistent with the risk information described in the general investigational plan or elsewhere in the current application.

**Life-threatening:** An AE or SAR is considered “life-threatening” if, in the view of either the Investigator or sponsor, its occurrence places the patient or subject at immediate risk of death. It does not include an AE or suspected adverse reaction that, had it occurred in a more severe form, might have caused death.

**A SERIOUS ADVERSE EVENT (SAE)** is any AE or suspected adverse reaction occurring at any dose that:

- Results in death.
- Is life-threatening.
- Results in a persistent or significant incapacity or substantial disruption of the ability to conduct normal life functions.
- Requires inpatient hospitalization.
- Prolongs inpatient hospitalization.
- Is a congenital anomaly/birth defect.
- Is a significant medical event (i.e., one that may jeopardize the subject or may require intervention to prevent one or more of the other outcomes listed above).

**A NON-SERIOUS ADVERSE EVENT** is any AE that does not meet the definitions for SAEs as described above.

Each AE will be classified as **SERIOUS or NON-SERIOUS** using the definitions provided above.

The **SEVERITY** of each AE will be classified as **MILD, MODERATE, or SEVERE**.

The Investigator will review each event and assess its **RELATIONSHIP** to use of investigational product (unrelated, unlikely, possibly, probably, definitely). The AE will be assessed using the following definitions:

**Unrelated:**

- Event occurring before dosing.
- Event or intercurrent illness due wholly to factors other than investigational product use.

**Unlikely:**

- Poor temporal relationship with investigational product use.
- Event easily explained by subject's clinical state or other factors.

